6.1.5 EFFICACY ENDPOINTS

6.1.5.1 Main Efficacy Endpoint

The main endpoint will be based upon changes in the CGI, which shall be based on the aggregate of all testing as reviewed and interpreted by the Investigator. Comparisons between the different active treatment arms will be made, as will comparisons between the active treatment arms and the placebo arm.

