2.2.2 SECONDARY OBJECTIVES

To document the PK and PD of L1-79 in a repeated dosing clinical situation, and to assess any change from baseline in the core symptoms of autism and associated behaviors using various standardized, validated ASD assessment instruments, and by comparing the results of subjects randomized to receive 1 of 3 different dosage levels of L-79 against placebo in a double-blind fashion. Also, changes in the ADOS core, including the severity scale, and the Clinical Global Impressions scale (CGI), including severity and improvement subscales will be assessed.

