3.0 DESIGN AND METHODS

3.1 Study Design

This is a five-arm design that incorporates 2 open label groups whose doses are known for the purpose of understanding PK/PD and to determine if there are any EKG changes associated with the administration of L1-79, and a 3-group prospectively randomized, double-blind, trial of L1-79 at 2 dosage levels versus placebo.

Two dosages of L1-79 will be tested in this study: 100 mg t.i.d. and 200 mg t.i.d. The investigators in this study have the most experience with these two dosages during exploratory use of L1-79 described above. In preliminary observations in a number of patients between the ages of 2.75 and 24 years of age doses between 90 to 400 mg t.i.d. were well tolerated, and no evidence was found that suggests a need for weight based dosing. These findings were presented to the FDA.

The first cohort of 20 patients to be enrolled will all receive L1-79 100 mg t.i.d., and will be comprised of 3 groups of patients. The first 100 mg group will differ from the others in that they will get blood samples drawn for PK analysis and EKGs will be taken. The safety and PK data from this group will be submitted for FDA review and acceptance before the 200 mg t.i.d. cohort will be enrolled. The remaining 15 patients in this cohort will be randomized to receive either L1-79 100 mg t.i.d. or placebo on a 2:1 basis (2 L1-79 patients for each placebo patient). While the FDA is reviewing the data from the first 5 patients all 100 mg t.i.d. patients will continue to be treated.

The second cohort is identical to the first. The initial 5 patients to be enrolled will differ from the others in that they will get blood samples drawn for PK analysis and EKGs will be taken. The safety and PK data from this group will be submitted for FDA review and acceptance. The remaining 15 patients in this cohort will be randomized to receive either L1-79 200 mg t.i.d. or placebo on a 2:1 basis (2 L1-79 patients for each placebo patient). While the FDA is reviewing the data from the first 5 patients all enrolled patients will continue to be treated

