5.1.1 ASSIGNMENT OF PATIENTS TO GROUPS

At each of the two tested dosage levels, the first 5 patients in each group will be assigned to receive the specified dose of either 100 mg t.i.d. or 200 mg t.i.d., whereas the following 15 patients in that group will be randomized to receive the specified dosage or placebo. After being assigned to a treatment arm each patient will be assigned a study number comprised of a 2-digit site identifier and a 3-digit patient identifier.

No patient will receive more than 100 mg t.i.d until permission to escalate to 200 mg t.i.d. is obtained from the FDA after their review of the first week of safety and PK data from the 100 mg group. This permission will follow if the safety data submitted for the first week of dosing in the Assigned Dosage Group is assessed by the FDA to be sufficiently safe to allow for a dosage escalation.

Each study site will be identified by a 2-digit number beginning with 01. Each patient screened for admission into the study will be assigned a unique sequential number that also identifies their study site. Thus, the 1st patient enrolled in the first study site will be patient 01-001 and the 2nd patient enrolled at the 2nd study site will be patient 02-002.

Study numbers will not be assigned until a patient is qualified and entered into the trial. Screening failures will not be assigned numbers. However, a list of screen failures and their demographic data will be maintained by the Investigator.

Patients will be enrolled and receive their first dose within 3 weeks of completing the screening procedure.

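### The 100 mg versus 200 mg comparison is not randomised, and each dose against the single placebo group carries half of any cohort difference, because the design is two separate 2:1 randomisations

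*Combined protocol and SAP*

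**What the plan says.** Section 6.1.5.1 plans, for the CGI: "Comparisons between the different active treatment arms will be made, as will comparisons between the active treatment arms and the placebo arm". Placebo is a single arm there, and the Synopsis lists it as one group, Group 5, with 10 patients.

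Section 3.1 introduces the randomised part as "a 3-group prospectively randomized, double-blind, trial of L1-79 at 2 dosage levels versus placebo", then describes two cohorts. In the first, 15 patients are "randomized to receive either L1-79 100 mg t.i.d. or placebo on a 2:1 basis". In the second, 15 are "randomized to receive either L1-79 200 mg t.i.d. or placebo on a 2:1 basis". Data from the first open-label group go to the FDA "before the 200 mg t.i.d. cohort will be enrolled", and Section 5.1.1 repeats the gate: "No patient will receive more than 100 mg t.i.d until permission to escalate to 200 mg t.i.d. is obtained from the FDA". Sections 4.3 and 5.1.3 describe the same two-step scheme.

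Other sections describe the randomisation differently:
- Section 2.2.2 speaks of "comparing the results of subjects randomized to receive 1 of 3 different dosage levels of L-79 against placebo", although only two doses are studied.
- Section 5.9.1.1 has patients randomised among four groups.
- Sections 5.9.1.3 and 5.9.2.2 describe random assignment to dosage groups.
- Section 4.0 counts 15 randomised patients per dose, which includes the five open-label patients.
- The Synopsis has placebo patients from Group 2's randomisation under treatment during the FDA review, but also makes Groups 3 to 5, which include all placebo patients, wait for that review.

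Section 6.1 limits the analysis to descriptive statistics and defers a formal statistical plan. No section stratifies by cohort or restricts a comparison to concurrent placebo.

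**The concern.** A direct comparison of 100 with 200 mg compares patients from two different randomisations. Any difference between the cohorts that is unrelated to dose (period, patient mix, rating habits) enters that comparison as if it were a dose effect. A single placebo group of 10 that mixes the two cohorts also brings part of that difference into each dose-versus-placebo comparison, with opposite signs, so an apparent dose response could be created or hidden. The CGI is an Investigator's overall judgement, which makes a shift between cohorts conceivable. The three-group label and the wording in Sections 2.2.2, 5.9.1.1, 5.9.1.3 and 5.9.2.2 could lead whoever writes the deferred plan to treat the study as one three-arm randomisation.

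**Working it through.** **Inputs.** From the Synopsis and Sections 3.1 and 5.1.3: per cohort, 5 open-label patients and 15 randomised 2:1. From Section 6.1.1: efficacy is analysed in all randomised subjects, so the open-label patients are not counted below. Assumptions, not in the documents: an additive cohort shift d of 0.2, 0.5 or 0.8 SD (cohort 2 minus cohort 1), and a common SD of 1.

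**Step 1: reproduce the plan's figures.** Per cohort: 5 + 10 + 5 = 20. Two cohorts: 40. Placebo: 5 + 5 = 10. Both totals match the Synopsis.

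**Step 2: can anyone be allocated to either dose?** A cohort 1 patient can receive 100 mg or placebo; a cohort 2 patient, 200 mg or placebo. Neither randomisation offers both doses.

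**Step 3: bias.** Bias = d × (share of first arm in cohort 2 − share of second arm in cohort 2).

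**Step 4: precision.** SE = sqrt(1/n1 + 1/n2) in SD units. For the difference between the two placebo-adjusted effects, SE = sqrt(2 × (1/10 + 1/5)).

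| Comparison | Patients | Bias | SE (SD units) |
|---|---|---|---|
| 200 vs 100 mg, direct | 10 vs 10 | (1 − 0)d = d | 0.447 |
| 200 mg vs single placebo group | 10 vs 10 | (1 − 0.5)d = +d/2 | 0.447 |
| 100 mg vs single placebo group | 10 vs 10 | (0 − 0.5)d = -d/2 | 0.447 |
| Each dose vs own cohort's placebo | 10 vs 5 | 0 | 0.548 |
| All active vs all placebo | 20 vs 10 | (0.5 − 0.5)d = 0 | 0.387 |
| 200 vs 100 mg, placebo-adjusted | 10, 5, 10, 5 | 0 | 0.775 |

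**Step 5: put in the assumed d.** With d = 0.2 / 0.5 / 0.8 SD and equally effective doses, the direct dose comparison shows a difference of 0.2 / 0.5 / 0.8 SD. Each dose against the single placebo group is off by 0.10 / 0.25 / 0.40 SD, downward for 100 mg and upward for 200 mg.

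**Step 6: price of removing the bias.** Own-cohort placebo: 0.548/0.447 = 1.22, 22% wider. Placebo-adjusted dose contrast: 0.775/0.447 = 1.73, 73% wider, with a 95% half-width of 1.96 × 0.775 = 1.52 SD against 1.96 × 0.447 = 0.88 SD.

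**Step 7: the other reading of the Synopsis.** If all 10 placebo patients started after the gate, the placebo share in cohort 2 would be 1. Bias would then be (0 − 1)d = -d for 100 mg, 0 for 200 mg, and (0.5 − 1)d = -d/2 for all active against all placebo; 100 mg would have no placebo patients from its own cohort. The results in Step 3 therefore depend on the 5 + 5 split in Section 3.1.

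**The case against.** Safety is the primary endpoint, the efficacy analysis is descriptive, and a statistical plan is still to come. Section 6.1.5.1 does not say that placebo will be pooled across cohorts, and Section 4.3 speaks of two placebo-controlled arms, which fits cohort-specific placebo. Own-cohort comparison also costs precision. In squared-error terms, dose versus placebo has d²/4 + 0.2 with all placebo and 0.3 within cohort; the dose contrast has d² + 0.2 direct and 0.6 adjusted. Both pairs are equal at d = sqrt(0.4) = 0.63 SD, and below that the direct and pooled comparisons are closer to the truth on average.

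The trade-off stands: it is a reason to keep the pooled display beside the within-cohort one. The rest does not remove the point. A descriptive difference can be just as biased, nothing binds the later plan to account for cohort, and the singular placebo arm with one Group 5 of 10 makes pooling the natural reading.

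A reader might go further than the documents allow:
- *That every planned comparison is confounded.* All active against all placebo is not, because both cohorts use 2:1, and each dose against the full placebo group carries only half the shift.
- *That the cohorts run strictly one after the other.* The gate needs first-week data from the five Group 1 patients only, and cohort 1 treatment continues during the review, so the cohorts may overlap. Overlap still does not randomise between doses.
- *That cohort 1 results will be unblinded while cohort 2 is being rated.* Section 5.1.4 restricts when the code may be broken and leaves the word group undefined.
- *That a period effect is documented.* Questions about school and home are put to every patient and show no shift.
- *That the dose comparison will be presented as randomised.* Section 6.1.5.1 does not call it so.

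**Conclusion.** The point holds for two of the planned comparisons. The comparison of 100 with 200 mg is non-randomised and carries any cohort shift in full. Each dose against the single placebo group carries it at half strength and in opposite directions, given five placebo patients per cohort. The size of the shift is unknown; 0.2 to 0.8 SD is an assumed range. Because the analysis is descriptive, the harm is that a cohort difference may be read as a dose effect; no stated error rate or power is affected. Sequential escalation is not itself the fault. Removing the bias from the dose contrast leaves a 95% half-width of about 1.5 SD, so the study can say little about dose response however it is displayed.

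**What to change.** In Section 6.1.5.1, and in the deferred statistical plan before any cohort is unblinded:
- show the placebo group split by cohort;
- present each dose against the placebo patients randomised in its own cohort, beside the pooled-placebo display;
- label 100 versus 200 mg as a non-randomised, between-cohort comparison.

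Reconcile the three-group label in Section 3.1, the three dosage levels in Section 2.2.2, the randomised counts in Section 4.0, the four groups in Section 5.9.1.1, and the assignment wording in Sections 5.9.1.3 and 5.9.2.2 with the two randomisations set out in Sections 3.1, 4.3, 5.1.1 and 5.1.3. The two Synopsis statements on when placebo patients may start must also be reconciled, since Step 7 of the working shows that the comparisons depend on the answer.

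The cost is wording and a table column, plus the wider standard errors in Step 6 for the cohort-specific displays. Sample size and allocation stay as they are.

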6.1.5.2 Secondary Efficacy Endpoints

- Analysis of individual psychometric test scores over time
- Multivariate analysis of psychometric test panel over time
- Physicians grading of improvement over time
- Correlations of test scores with each other and with Investigator assessment

6.1.5 OTHER ENDPOINTS

Pharmacokinetic and pharmacodynamic data will be presented for the Assigned Dosage Group patients

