APPENDIX E: SAMPLE COLLECTION METHODS.....		58
APPENDIX F: DSM-5 DIAGNOSTIC CRITERIA FOR AUTISM SPECTRUM DISORDER		59

RESTRICTED DISTRIBUTION OF PROTOCOLS

- This protocol contains information that is confidential and proprietary. The information contained herein is provided for the purpose of conducting a clinical trial in collaboration with [name].
-
- The contents of this protocol may be disclosed to study personnel under your supervision and to your Institutional Review Board(s). The contents of this protocol may not be disclosed to any other parties (unless such disclosure is requested by [name]).

PROTOCOL SYNOPSIS

- Study Drug: L1-79
- Protocol Number: HT 02-121

Protocol Title: A Phase 2 Safety Study of L1-79 in the Treatment of Autism

- Study Phase: 2
- **Study Design:** This study has a dose escalating cohort design. Treatment arms consist of L1-79 at doses of 100 mg t.i.d (or placebo), or 200 mg t.i.d., (or placebo). Pharmacokinetics will be assessed in initial cohorts of 5 patients for each dose group followed by a double blinded, placebo-controlled assessment of PK/PD and safety in a cohort of 15 patients randomized 2:1 active to placebo. Groups 1& 2 below can start simultaneously. While the FDA is reviewing the data from Group 1, Groups 2 and the placebo patients randomized with Group 2 will be ongoing. All 5 subjects assigned to Group 1 (100 mg L1-79) must have completed the PK portion of the study with results analyzed and accepted by the FDA before subjects in Groups 3-5 can begin treatment.
- Sample Size: N=40
 - Group 1 (n=5) 100 mg L1-79 (1x100mg capsule+1 placebo capsule)
 - Group 2 (n=10) 100mg L1-79 (1x100mg capsule+1 placebo capsule)
 - Group 3 (n=5) 200 mg L1-79 (2x100 mg capsules)
 - Group 4 (n=10) 200 mg L1-79 (2x100 mg capsules)
 - Group 5 (n=10) Placebo (2 placebo capsules)

All Groups will receive the assigned study drug three-times daily.

- **Study Population:** Male subjects with autism between the ages of 13 and 21 years of age who meet the entry criteria and who are able to complete standardized measures allowing them to participate in this study.

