5.5.1.7 Concomitant Medications

As documented in the history and at the screening visit, no patient currently receiving polytherapy for autism will be enrolled in this trial. Any agent which is being prescribed for the treatment of ASD will be noted as such in the eCRF. Subjects identified for accrual into this trial will be weaned to the lowest dose of any prescribed psychotropic medication over the two to four weeks preceding their screening visit deemed effective by the Investigator.

All prescription and nonprescription medication taken by the patient from 14 days prior to screening and up to and including the final visit will be recorded in the medical record and on the eCRF. Any addition, deletion, or change in the dose of these medications must be recorded.

Because the mechanism of L1-79 is the inhibition of catecholamine synthesis, the potential exists for interactions with neurologically active, and other, drugs. Investigators will be diligent in observing potential drug interactions and should appropriately reduce the dose of any concomitant medication that is observed to be potentiated in the presence of L1-79.

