5.5.1.8 Clinical Laboratory Safety Assessments

The following parameters will be measured for the Randomized Groups at screening, at week 4, and at the 4-week follow-up, and in addition for the Assigned Dosage Groups at each weekly visit and the 1 Week Follow up using the central laboratory provided:

- Urinalysis
 - Color
 - Clarity/turbidity
 - pH
 - Specific gravity
 - Glucose
 - Ketones
 - Nitrites
 - Bilirubin
 - Urobilirubin
 - Blood
 - Protein
 - RBC
 - WBC
 - Squamous epithelial cells
 - Casts
 - Crystals
 - Bacteria
 - Yeast
 - Fractionated urinary catecholamines
 - Vanillylmandelic acid
- Hematology
 - hemoglobin,
 - hematocrit,
 - platelet count,
 - RBC
 - WBC with differential
- Serum Chemistry
 - sodium,
 - potassium,
 - chloride,
 - BUN,
 - creatinine,
 - AST,
 - ALT,
 - GGT,
 - LDH,
 - CO₂/bicarbonate
 - total protein,
 - albumin,
 - calcium,

- phosphorous,
- alkaline phosphatase,
- total bilirubin (direct, indirect, total),
- cholesterol,
- triglyceride,
- amylase, lipase
- T₄ & TSH
- Fractionated Plasma Catecholamines
- Metanephhrines, plasma free & fractionated.

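### Pharmacodynamics are to be presented only for the open-label groups, so no active-versus-placebo PD comparison is planned, although the synopsis promises one and catecholamine markers are scheduled in every randomised patient

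*Combined protocol and SAP*

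**What the plan says.** PD is part of the secondary objective (Section 2.2.2) and a secondary endpoint (synopsis, Study Endpoints). The documents then describe it in different ways.

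- The synopsis (Study Design) says the open-label PK cohorts are followed by a "double blinded, placebo-controlled assessment of PK/PD and safety in a cohort of 15 patients randomized 2:1 active to placebo".
- Section 3.1 makes PK/PD a purpose of the two open-label groups. Sections 5.1.2 and 5.9.3.1 tie PD to blood levels of L1-79 in those groups.
- Section 6.1.5 (Other Endpoints) is one sentence: "Pharmacokinetic and pharmacodynamic data will be presented for the Assigned Dosage Group patients".
- Section 5.5.1.8 opens: "The following parameters will be measured for the Randomized Groups at screening, at week 4, and at the 4-week follow-up". Its list includes "Fractionated urinary catecholamines" and "Vanillylmandelic acid" under urinalysis, and "Fractionated Plasma Catecholamines" and "Metanephhrines, plasma free & fractionated" under serum chemistry. Appendix A marks serum chemistry and urine analysis for all patients at the same three visits.
- Section 5.1.3 exempts randomised patients from PK samples, EKGs and the 1-week follow-up, but not from these laboratory tests.
- Section 6.1.4 plans tables and graphs of change from baseline in safety laboratory values, naming hematology and serum chemistry. Only its EKG item is limited to the Assigned groups.
- Section 6.1 makes the analysis descriptive and defers a formal statistical plan until before treatment is completed.

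**The concern.** The listed analytes are the natural PD markers for this drug. Section 5.5.1.7 gives the reason: "Because the mechanism of L1-79 is the inhibition of catecholamine synthesis". If Section 6.1.5 is followed as written, the secondary PD objective is answered only from change over time in 5 open-label patients at each dose. Such a change cannot separate a drug effect from diet, stress, assay variation or regression to the mean. The trial has a randomised placebo group in which the same analytes are scheduled, and the analysis text does not use that group for PD. Since Sections 5.1.2 and 5.9.3.1 describe PD through L1-79 levels, Section 6.1.5 could even be met without presenting any catecholamine result.

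**Working it through.** **Group sizes.** The synopsis gives 5 + 10 + 5 + 10 + 10 = 40, which reproduces its N=40. Randomising 15 patients 2:1 gives 10 active and 5 placebo per cohort, so 10 placebo over two cohorts. There is no power-based figure to reproduce: the documents give no alpha, power, effect size or SD.

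**Coverage of the PD presentation.** Section 6.1.5 covers 5 + 5 = 10 of 40 patients (25%), none on placebo. It leaves out 30 randomised patients (75%), who have 30 × 3 = 90 scheduled laboratory time points at screening, Week 4 and follow-up.

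**Where each marker would be shown.**

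| Marker | Filed in 5.5.1.8 under | Named in the 6.1.4 safety display? | Planned PD comparison with placebo? |
|---|---|---|---|
| Plasma catecholamines | Serum chemistry | Yes, through serum chemistry | No |
| Plasma metanephrines | Serum chemistry | Yes, through serum chemistry | No |
| Urinary catecholamines | Urinalysis | No | No |
| VMA | Urinalysis | No | No |

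Section 6.1.4 states no active-versus-placebo comparison, whereas Section 6.1.5.1 does so for the CGI.

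**Precision.** The SD of change is not given, so it is set to 1. Complete data are assumed, and half-widths are for 95% intervals.

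- One open-label group, uncontrolled change: t(0.975, 4)/√5 = 1.24.
- One dose (10) against its concurrent placebo (5), variance pooled over the four randomised cells (30 − 4 = 26 df): t(0.975, 26) × √(1/10 + 1/5) = 1.13.
- One dose (10) against all placebo (10): t(0.975, 18) × √(2/10) = 0.94. This borrows placebo patients from the other cohort, which lies across the FDA review step.
- Both doses (20) against placebo (10), stratified by cohort: each cohort has variance 0.30, and their mean has variance (0.30 + 0.30)/4 = 0.15, so t(0.975, 26) × √0.15 = 0.80.

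The first figure is a within-patient change at one dose. The others are differences between arms, so they do not measure the same quantity. The closest pairing, one dose against concurrent placebo, is only about 9% narrower (1.13 against 1.24).

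**The case against.** A reader might infer that the placebo-controlled PD data go unused. The documents do not support that for the plasma markers. They are filed under serum chemistry, and Section 6.1.4 displays changes in that panel without limiting them to the Assigned groups, so placebo patients' values would be seen. What is missing is a PD comparison of arms, together with any named display for the urinary markers.

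The documents also never name these analytes as PD markers; Section 5.5.1.8 lists them as safety tests. Section 6.1.5 agrees with Sections 3.1, 5.1.2 and 5.9.3.1, and the synopsis is the outlier. This stands: the choice of markers is inferred from the stated mechanism. It also shows that PD is undefined, which is itself a gap.

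Nor is the change wholly free. A 24-hour urine collection is specified only for the Assigned groups (Sections 5.9.2.2 and 5.9.3.1). Randomised patients give urine for safety analysis by an unstated method, so the urinary markers may not be comparable across groups. Section 5.5 specifies local laboratories and Section 5.5.1.8 a central one. Draw time relative to dose is not fixed in randomised patients. These limits stand, and they favour the plasma markers.

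Finally, the study is descriptive and a formal plan is still to come. An estimate with an interval by arm fits a descriptive study, and the later plan would otherwise inherit the restriction in Section 6.1.5.

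**Conclusion.** The point holds as a gap and an inconsistency in the plan. PD presentation is confined to 10 uncontrolled patients, against the synopsis, while the relevant analytes are scheduled in 30 randomised patients, 10 of them on placebo. A reader might also expect a gain in precision, but the figures do not show one for a single dose: half-widths of about 1.13 SD (one dose, concurrent placebo) and 0.80 SD (doses pooled, stratified by cohort) remain wide. The benefit is a randomised control, and the evidence would be supportive only. The conclusion rests on reading the catecholamine-pathway analytes as the PD markers. The half-widths rest on complete data and a common SD of change, which the documents do not state.

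**What to change.** - Name plasma catecholamines and metanephrines, and urinary catecholamines and VMA, as the PD markers.
- Change Section 6.1.5 (Other Endpoints) to present PD for all patients. Give a descriptive summary, with estimates and 95% CIs and no hypothesis tests, of the change on the log scale from screening to Week 4 by randomised arm against placebo, accounting for screening value and cohort.
- Make the plasma markers the main comparison. Include urinary markers across groups only if the randomised patients' collection method is stated and comparable with the 24-hour collection in the Assigned groups.
- Label the Day 56 value as off-drug, and show the open-label groups separately.
- Keep PK for the Assigned groups only. Reconcile the synopsis (Study Design) with Sections 3.1, 5.1.2, 5.9.3.1 and 6.1.5.
- State whether these assays are run locally or centrally, reconciling Sections 5.5 and 5.5.1.8.

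For the plasma markers the cost is one paragraph and one table from samples already scheduled. The urinary markers may also need a change to the collection procedure. The unfixed draw time and the small groups remain as limits to be stated with the results.
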